8.3 Adverse Events and Serious Adverse Events

The definitions of an AE and a SAE are in [Appendix 4](#).

8.3.1 Time Period and Frequency for Collecting Adverse Event and Serious Adverse Event Information

The AE reporting period for safety surveillance begins when the participant is initially included in the study (from time of signature of the Prescreening ICF) and continues until Safety Follow-up Visit (30 ± 3 days after the last dose of tepotinib/osimertinib).

Any SAE assessed as related to study intervention must be recorded and reported, as indicated in [Appendix 4](#), whenever it occurs, irrespective of the time elapsed since the last administration of study intervention.

The method of recording, evaluating, and assessing causality of AEs (including SAEs) and the procedures for completing and transmitting SAE reports are in [Appendix 4](#).

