8.1.2 Analyses per Analysis Set

The following table summarizes the use of the analysis sets and the groups specified above to present the results of the different analysis in tables and figures.

Table 1. Analysis Sets: presentation of the results in tables and figures

Analysis	Analysis set	Results to be presented by
Baseline Characteristics, Baseline Biomarkers, Protocol Deviations, Previous or Concomitant Medications/Procedures	SAF	Tepotinib RP2Dmg + Osimertinib 80mg: T+, L+, Combined (T+ and/or L+), Other, Total Tepo+Osi Tepotinib 500mg: T+, L+, Combined (T+ and/or L+), Other, Total Tepo Total

Analysis	Analysis set	Results to be presented by
Efficacy (excluding sensitivity analyses, subgroup analyses, overall survival and QoL): primary and secondary endpoints	mFAS	Tepotinib RP2Dmg + Osimertinib 80mg: T+, L+, Combined (T+ and/or L+) Tepotinib 500mg: T+, L+, Combined (T+ and/or L+)
Efficacy (sensitivity analysis: start of subsequent anti-cancer treatment, study treatment discontinuation due to COVID-19, subgroup analyses, overall survival and QoL only): primary and some secondary endpoints	mFAS	Tepotinib RP2Dmg + Osimertinib 80mg: T+, L+, Combined (T+ and/or L+)
Efficacy (sensitivity analysis: all participants in the FAS): primary endpoint and some secondary endpoints	FAS	Tepotinib RP2Dmg + Osimertinib 80mg Tepotinib 500mg
Efficacy (Central Nervous System Tumor Response based on RANO- BM criteria): tertiary/exploratory endpoints	FAS/mFAS	Tepotinib RP2Dmg + Osimertinib 80mg: T+, L+, Combined (T+ and/or L+), Other, Total Tepo+Osi (as applicable according to whether FAS or mFAS is presented)
Safety: primary endpoint for the safety run-in	SRIAS	Tepotinib 500mg + Osimertinib 80mg
Safety: all other safety endpoints; Compliance and Exposure	SAF	Tepotinib RP2Dmg + Osimertinib 80mg: T+, L+, Combined (T+ and/or L+), Other, Total Tepo+Osi Tepotinib 500mg: T+, L+, Combined (T+ and/or L+), Other, Total Tepo
Listings (excluding enrollment)	SAF or FAS	SAF for listings presenting baseline and safety data FAS for efficacy listings

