9.3 Definition of On-treatment Periods

Participants in the monotherapy arm will be allowed to switch to the combination treatment once PD is confirmed. The following on-treatment periods are defined in order to indicate which data will be used for the analyses.

Table 3.	On-treatment Periods
----------	-----------------------------

		Combination Arm	Monotherapy Arm - No Switch	Monotherapy Arm – Switch ^a
Period 1	Start	First dose of study treatment	First dose of study treatment	First dose of study treatment
	End	Last dose of study treatment + 30 days or the cut-off date or death, whichever occurs first	Last dose of study treatment + 30 days or the cut-off date or death, whichever occurs first	First dose of osimertinib ^b
Period 2	Start	NA	NA	First dose of osimertinib ^b
	End	NA	NA	Last dose of combination treatment ^c + 30 days or the cut-off date or death, whichever occurs first

a: Unless stated otherwise, data from Period 1 will contribute to tables, figures and listings whereas data from Period 2 to study discontinuation will only be listed.

b: Measurements collected on the day of the start of the combination treatment will be considered to belong to Period 1 unless clearly collected after the first administration of osimertinib. The same rule applies to adverse events.

c: The last dose of the combination treatment is considered as the last dose of tepotinib or osimertinib, whichever is later.

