TEAEs are those events that started during the on-treatment periods (see Section 9.3), or before Period 1 and worsened during the on-treatment periods. This includes also AEs ongoing at baseline, which first improve under study treatment and then worsen irrespective of baseline. The rules defined in Table 10 will be used to assign TEAEs to the on-treatment periods. Any AE occurring before Period 1 and resolved before Period 1 or not worsening during the on-treatment periods will be included in the AE listings, but will not be included in the TEAE summary tables (unless otherwise stated). Adverse events with changes in toxicity grade are recorded as separate entries in the eCRF with associated end and start dates (start date equals end date of previous entry, supported in eCRF by 'AENEWID' in SUPPAE). Records of the same AE will be considered as one event in the analysis. These events will be kept as separate records in the database in order to maintain the full detailed history of the events. In AE listings, records that are part of the same AE will be grouped together and presented in chronological order. If the severity of the reported event worsens after start of treatment, the TEAE flag will be re-evaluated for the worse and the subsequent records as per the TEAE definition: once one record is considered treatment emergent, all the subsequent records will be considered treatment emergent too, even if starting after the ontreatment periods.

All analyses described in Sections 15.2.2 and 15.2.3 will be based on TEAEs belonging to Period 1, if not otherwise specified. The AE listings will include all AEs (whether treatment emergent or not). A flag will be added to indicate if the AE is treatment emergent and in which period.

Unless otherwise specified, TEAEs will be summarized by number and percentage of participants with the TEAE in the category of interest and sorted by primary SOC and PT in alphabetic order.

Each participant will be counted only once within each SOC or PT. If a participant experiences more than one AE within an SOC or PT for the same summary period, only the AE with the strongest relationship or the worst severity, as appropriate, will be included in the summaries of relationship and severity.

Table 10.	Assignment of TEAEs to the on-treatment periods

	TEAE in Period 1	TEAE in Period 2
Starts before Period 1 and worsens during Period 1	Х	
Starts before Period 1 and worsens during Period 2		Х

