Starts in Period 1 (regardless of worsening in Period 2)	Х	
Starts in Period 2		Х

15.2.2All Adverse Events

Adverse Event information is collected on the "Adverse Events Details" eCRF page.

Adverse events will be summarized by worst severity (according to NCI-CTCAE version 5.0) per participant, using the latest version of MedDRA PT as event category and MedDRA primary SOC body term as Body System category.

In case a participant has events with missing and non-missing grades, the maximum of the nonmissing grades will be displayed. No imputation of missing grades will be performed.

The overall summary of AEs table will include the frequency (number and percentage) of participants with each of the following:

- TEAEs
- Study treatment related TEAEs (any study treatment and by study treatment components)
- Serious TEAEs
- Study treatment related serious TEAEs (any study treatment and by study treatment components)
- TEAEs with NCI-CTCAE Grade \geq 3 and \geq 4
- Study treatment related TEAEs with NCI-CTCAE Grade ≥ 3 and ≥ 4 (any study treatment and by study treatment components)
- TEAEs leading to death
- Study treatment related TEAEs leading to death (any study treatment and by study treatment components)
- Adverse Events of Special Interest (AESIs)

Adverse events of special interest are defined as events suggestive of drug-induced liver injury including hepatic / liver failure and hepatitis (non-infectious). Adverse Events of Special Interest (AESI) will be identified according to a pre-specified search list provided by the Sponsor Safety Lead using the last available version of MedDRA Preferred Terms at the time of each analysis.

In addition, the following tables summarizing the frequency of participants with TEAEs by SOC and PT will be produced:

- TEAEs
- Study treatment related TEAEs (any study treatment and by study treatment components)
- Serious TEAEs
- Non-serious TEAEs applying a frequency threshold of 5%
- Study treatment related serious TEAEs (any study treatment and by study treatment components)
- TEAEs by worst NCI-CTCAE Grade (Any, ≥ 3 , ≥ 4 and 5)
- Study treatment related TEAEs by worst NCI-CTCAE Grade (Any, ≥ 3 , ≥ 4 and 5) (any study treatment and by study treatment components)

- TEAEs leading to death
- Study treatment related TEAEs leading to death (any study treatment and by study treatment components)
- Adverse Events of Special Interest (AESIs)

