15.3.2 Serious Adverse Events

Please see Section 15.2.2 for the analysis of serious TEAEs.

A listing of serious TEAEs will also be provided.

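### A new drug-related SAE that starts after the 30-day on-treatment window must be recorded under the protocol, yet it enters no SAE count and is not in the SAE listing

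*SAP*

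**What the plan says.** **Collection.** Under Protocol 8.3.1 the general AE reporting period starts at Prescreening consent and "continues until Safety Follow-up Visit (30 ± 3 days after the last dose of tepotinib/osimertinib"). SAEs assessed as related to study intervention are treated differently. They must be recorded and reported "whenever it occurs, irrespective of the time elapsed since the last administration of study intervention".

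**Window.** In SAP 9.3 (Table 3) the on-treatment period of the combination arm, and of monotherapy participants who do not switch, ends at "Last dose of study treatment + 30 days or the cut-off date or death, whichever occurs first". For participants who switch, Period 2 ends by the same rule, counted from the last combination dose. SAP 15.2.1 then defines the event set: "TEAEs are those events that started during the on-treatment periods (see Section 9.3), or before Period 1 and worsened during the on-treatment periods".

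**Outputs.** SAP 15.2.1 sets the default: "All analyses described in Sections 15.2.2 and 15.2.3 will be based on TEAEs belonging to Period 1, if not otherwise specified". The SAE entries in the overall summary and in the tables by SOC and PT (SAP 15.2.2) are all worded as serious TEAEs, with or without relationship to study treatment. The listings named in 15.2.2 are AEs, AESIs and serious TEAEs. SAP 15.3.2 repeats the last of these: "A listing of serious TEAEs will also be provided". SAP 15.2.1 nevertheless states that AE listings hold every AE, treatment emergent or not, with a flag for treatment emergence and period.

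**The concern.** The protocol lifts the time limit for one class of event only, the SAE judged related to study drug. That is the class for which the SAP's dedicated outputs stop at 30 days. Of the three listings named in SAP 15.2.2, those for AEs and AESIs are not worded as treatment emergent only. The one for serious events is, so the most important category has the narrowest listing.

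At stake is how easily a delayed drug-related harm can be seen. Protocol 2.3 names interstitial lung disease as an important identified risk with possible mortality. A related, non-fatal lung event that begins after the window would be recorded, but a reader of the SAE tables and SAE listing would not meet it.

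**Working it through.** The plan states no figure on this point, so the check follows one case through the SAP's rules: an SAE judged related, newly starting on day 31 or later after the last dose.

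| Step or output | Source | Rule | Result for this case |
|---|---|---|---|
| Collected? | Protocol 8.3.1 | No time limit for related SAEs | Yes |
| In the on-treatment period? | SAP 9.3, Table 3 | Ends at last dose + 30 days at the latest | No |
| Treatment emergent? | SAP 15.2.1 | Must start in the period, or start before Period 1 and worsen in the period | No |
| SAE rows of the overall summary | SAP 15.2.2 | Serious TEAEs, related serious TEAEs | Not counted |
| SAE tables by SOC and PT | SAP 15.2.2 | Same | Not counted |
| SAE listing | SAP 15.2.2 and 15.3.2 | Serious TEAEs | Absent |
| Listing of all AEs | SAP 15.2.1 and 15.2.2 | All AEs, flagged | Present, flagged as not treatment emergent |
| AESI listing | SAP 15.2.2 | Liver events found by the AESI search | Present only if it qualifies |
| Death tables and listing | SAP 15.3.1 | Deaths; fatal AEs named | Present only if fatal |

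**Carry-forward rule.** SAP 15.2.1 keeps later records of an event treatment emergent once an earlier record is. That covers a late change in an existing event, but not a new event.

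**Edge of ordinary reporting.** The Safety Follow-up Visit may fall as late as 30 + 3 = 33 days after the last dose, while the window closes at day 30. Any SAE starting on days 31 to 33, before a late visit, is also inside the protocol's reporting period and outside every SAE output.

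**Size.** The inputs are about 120 enrolled and 12 centrally confirmed monotherapy participants (Protocol 9.2).

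- Combination participants: 120 − 12 = 108. This is approximate, because randomization stops at 12 centrally confirmed participants, and locally positive but unconfirmed participants may add to the monotherapy arm.
- One participant: 1/108 = 0.93%, about 0.9 percentage points.

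The tables count participants, so this applies only to a participant with no other related SAE inside the window. The documents give no number of such participants. One to three, an assumption for illustration only, would be 1/108 = 0.9 to 3/108 = 2.8 points.

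**The case against.** The strongest reply is that the protocol itself asks for this analysis. Protocol 9.4.2 lists SAEs and related SAEs among the subtypes of TEAEs, with onset up to 30 days after the last dose, and the SAP implements that. Protocol 8.3.1 governs collection and reporting, not tabulation. After the Safety Follow-up Visit only related SAEs are collected, so a fixed window gives rates with uniform ascertainment. This stands, and it is why the treatment-emergent tables need not change.

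It is also true that the events are reported somewhere. A reader might infer that late related SAEs vanish from the study report. The documents do not support that, since the flagged listing of all AEs, the AESI listing and the death outputs each pick up some or all of them.

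A reader might also infer that the reported related-SAE count can only be too low. The omission does act in that direction, but other rules act the other way. A missing relationship is counted as related (SAP 15.2.1, with one exception for osimertinib in Period 1 of switchers). A completely missing onset date is generally set to the start of treatment (SAP 9.9). Records after the window stay treatment emergent once an earlier one is. The net direction for the whole count is not established.

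What the reply does not answer is the listing. Nothing in Protocol 9.4.2 requires the SAE listing to be cut at the window, and SAP 15.2.1 says that AE listings are not.

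**Conclusion.** The gap is real and narrow. A new, non-fatal, related SAE starting after the on-treatment period appears in no SAE count and not in the SAE listing, and the SAP's wording on listings is inconsistent with itself. The remedy concerns visibility and a separate count; the treatment-emergent analysis is sound.

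The size cannot be known from the documents. The 0.9 points per participant rests on the approximate 108 and on that participant having no related SAE within the window. It is not a cost per event: a late SAE in someone already counted changes no related-SAE percentage.

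A wider reading is tempting at the other end of the window. AEs are collected from Prescreening consent, but Table 1 in SAP 8.1.2 assigns "SAF for listings presenting baseline and safety data", so one might infer that SAEs in people never treated are wrongly omitted. The documents do not support treating that as an error. Protocol 9.3 states that people who consent to Prescreening or Screening are analysed for disposition and nothing else, and the safety objectives concern treated participants. That is a declared choice of scope.

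**What to change.** 1. In SAP 15.2.2 and 15.3.2, change the listing of serious TEAEs to a listing of all SAEs, carrying the treatment-emergent and period flag already planned in 15.2.1. This also removes the conflict with the statement that AE listings include all AEs.
2. In the overall AE summary of SAP 15.2.2, add one row, by arm: number of participants with a study-treatment-related SAE starting after the on-treatment period. For monotherapy participants who switched, count from the end of Period 2 and footnote them.
3. Leave the treatment-emergent SAE tables as they are.

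The cost is a change of SAP wording, one table row and one widened listing, all from data the protocol already collects. The related-SAE picture may look slightly less favourable. The new row should be labelled as resting on related SAEs only, because other SAEs are not collected after the Safety Follow-up Visit.

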9.4.2 Safety Analyses

All safety analyses will be performed on the SAF. All analyses will be presented by treatment arm and by dose level, if applicable, and participants will be analyzed as treated.

The safety analyses will also be done purely descriptively.

Endpoint	Statistical Analysis Methods
Primary (for the safety run-in)	
Occurrence of DLTs	Refer to Section 4.1 for the definition of DLTs The number and percentage of participants in the DLT analysis set during the DLT observation period will be tabulated.
Secondary	
Occurrence of AEs and treatment-related AEs and deaths during the study	
Adverse events will be coded according to the latest available version of the Medical Dictionary for Regulatory Activities. Severity of AEs will be graded using the NCI-CTCAE (v5.0) toxicity grades. AEs related to study intervention will be defined as any AE considered as related to tepotinib and/or osimertinib. Missing classifications concerning study intervention relationships will be considered related to the study intervention.
 
Any TEAEs will be summarized, ie, those events that are emergent during treatment having been absent prior to treatment or worsened relative to the pretreatment state and with onset dates occurring within the first dosing day of study intervention until 30 days after the last dose of study intervention (or switch over to combination treatment, whichever occurs first for the tepotinib monotherapy arm). Adverse events occurring after switch over will be described separately, details will be specified in the IAP.
 
Following subtypes of TEAEs will be presented in summaries and tables according to System Organ Classes and Preferred Terms:
 
 • TEAEs • SAEs • TEAEs related to tepotinib and/or osimertinib • SAEs related to tepotinib and/or osimertinib • NCI-CTCAE Grade 3 or higher TEAEs • NCI-CTCAE Grade 3 or higher TEAEs related to tepotinib and/or osimertinib • TEAEs leading to tepotinib and/or osimertinib interruptions • TEAEs leading to permanent tepotinib and/or osimertinib discontinuation • TEAEs leading to deaths. • AESIs 
Deaths during the study will also be presented in summaries and tables.
 
Adverse events of special interest are defined as events suggestive of drug-induced liver injury including hepatic/liver failure and hepatitis (non-infectious) and are

Endpoint	Statistical Analysis Methods

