- Duration of therapy (months)
- Total number of 3-week cycles
- Cumulative actual dose (mg)
- Dose intensity (mg/3 weeks)
- Relative dose intensity (%)

All participants in the SAF analysis set will have the above parameters calculated per period. For those participants in the monotherapy arm who switch to the combination treatment, results for Period 2 will only be listed.

For the combination arm only, duration of therapy will also be calculated in terms of study treatment by taking into account the date of first and last dose of study treatment.

Duration of therapy and number of 3-week cycles

The duration of therapy is defined as

Duration of therapy (in months) =
$$\left(\frac{\text{Date of last dosing day - Date of first dosing day + 1}}{30.4375}\right)$$

The total number of 3-week cycles is defined as the duration of therapy (in weeks) / 3.

Cumulative actual dose

The cumulative actual dose (mg) per participant is the sum of the total doses that the participant received while on-treatment per period (i.e. total dose administered [mg]).

Dose intensity and relative dose intensity

The dose intensity and the relative dose intensity will be calculated for a 3-week cycle. The dose intensity (mg/3 weeks) is defined as

Dose intensity (mg/3 weeks) =
$$\left(\frac{\text{Cumulative actual dose (mg)}}{\text{Total number of 3 week cycles}}\right)$$

The relative dose intensity is defined as

Relative dose intensity (%) =
$$\left(\frac{\text{Actual dose intensity}}{\text{Planned dose intensity}}\right) \times 100$$
,

where

- Planned dose intensity (mg/3 weeks) = RP2D mg × 21 days for tepotinib in the combination treatment
- Planned dose intensity (mg/3 weeks) = 500 mg × 21 days for tepotinib in the monotherapy treatment
- Planned dose intensity $(mg/3 \text{ weeks}) = 80 \text{ mg} \times 21 \text{ days for osimertinib}$

Dose reductions

In the combination arm, participants may have a dose reduction to 250 mg for tepotinib, which is also the minimum possible dose in this study.

The per protocol dose for osimertinib is 80 mg, which can be reduced to 40 mg if necessary.

The number of participants with and without any dose reduction will be summarized.

Therapy delays

Delay will be defined as a number of days between two successive administrations greater than 1, i.e. date of current administration - date of previous administration >1.

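### Adverse events are tabulated by arm only as crude percentages, with no adjustment for time at risk, so monotherapy can look safer if it is observed for less time

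*SAP*

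**What the plan says.** SAP 15.2.1 sets the general rule that "TEAEs will be summarized by number and percentage of participants with the TEAE in the category of interest", counting each participant once per system organ class or preferred term. The analyses in SAP 15.2.2 and 15.2.3 "will be based on TEAEs belonging to Period 1, if not otherwise specified". SAP 15.2.2 applies the same metric to the main table: "The overall summary of AEs table will include the frequency (number and percentage) of participants with each of the following".

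The length of Period 1 depends on the arm (SAP 9.3, Table 3). For the combination arm, and for monotherapy participants who do not switch, it ends at "Last dose of study treatment + 30 days or the cut-off date or death, whichever occurs first". For those who switch it ends at the first osimertinib dose. SAP 9.3 explains that "Participants in the monotherapy arm will be allowed to switch to the combination treatment once PD is confirmed". Protocol 9.4.2 sets the same limit on the TEAE window: 30 days after last dose, "or switch over to combination treatment, whichever occurs first for the tepotinib monotherapy arm".

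SAP 8.1.2, Table 1, row "Safety: all other safety endpoints; Compliance and Exposure", places the two arms in columns of the same tables.

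Three other outputs bear on observation time:
- SAP 13 tabulates duration of therapy, per drug and period.
- SAP 15.2.2 repeats the overall and the system organ class/preferred term tables with Periods 1 and 2 together if at least 6 participants switch.
- SAP 15.3.1 counts deaths within 60 days of first dose.

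Protocol 9.1 rules out a formal comparison of the arms, and both documents describe the safety analysis as descriptive.

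**The concern.** Safety of the combination and safety of monotherapy are separate secondary objectives, and their results stand in adjacent columns. The monotherapy arm was added to assess what tepotinib contributes to the combination (Protocol 2.2 and 4.2), so readers will look across the columns even though nothing is tested.

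The proportion of participants with an event grows with the time they are watched. If one arm is watched for less time, its percentages are lower whatever the drugs do, and the table cannot separate a difference in risk from a difference in observation. The protocol's own rationale suggests the direction: Section 4.2 argues that both MET and EGFR must be inhibited in this disease and describes flare after an EGFR inhibitor is stopped. That makes earlier progression on monotherapy plausible, but it does not say by how much.

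**Working it through.** **What the documents supply.** They give no expected time on either treatment and no adverse event rates, so there is no planned safety figure to reproduce. The usable facts are:
- the first scheduled scan at 6 weeks, about 1.4 months (Protocol 8.1);
- the 30-day tail (SAP 9.3);
- the primary analysis after at least 9 months on the combination, or death or discontinuation (Protocol 9);
- median progression-free survival of 4.2 and 16.6 months in the earlier tepotinib plus gefitinib study (Protocol 2.2);
- 12 monotherapy participants with centrally confirmed tissue positivity (Protocol 9.2).

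**Main illustration.** Assume the same constant hazard h per month in both arms. The crude proportion with an event by t months is 1 − exp(−h·t).

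| h per month | 1.5 mo (mono) | 2.5 mo (mono) | 6 mo (combo) | 8 mo (combo) |
|---|---|---|---|---|
| 0.05 | 7.2% | 11.8% | 25.9% | 33.0% |
| 0.10 | 13.9% | 22.1% | 45.1% | 55.1% |

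Smallest ratio over all pairings: 45.1/22.1 = 2.0. Largest: 33.0/7.2 = 4.6. The true hazard ratio is 1 throughout.

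**Wider assumptions.** With monthly risk p and fixed windows, the proportion is 1 − (1 − p)^t. Taking monotherapy at 1.4 to 4.2 months and the combination at 5 to 10 months including the tail:

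| Monthly risk | Smallest ratio (4.2 vs 5 mo) | Largest ratio (1.4 vs 10 mo) |
|---|---|---|
| 5% | 1.2 | 5.8 |
| 30% | 1.1 | 2.5 |
| 50% | 1.0 | 1.6 |

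The ratio cannot exceed the ratio of the two windows, and it falls towards 1 as events become common.

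**Variable stopping times.** Let time to stopping be exponential, with the window cut at 9 months, a one-month tail for the combination and none for monotherapy switchers. With medians of 1.4 to 4.2 months against 5.5 to 16.6 months, the ratio at 5% per month is 1.3 to 3.5. For example, medians of 2.1 and 8 months give 13.0% against 28.6%, ratio 28.6/13.0 = 2.2.

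**Share due to the switch rule.** Give both arms the same time to progression and remove only the one-month tail from monotherapy, at 5% per month:
- progression at 1.4 months: (1 − 0.95^2.4)/(1 − 0.95^1.4) = 0.116/0.069 = 1.67;
- progression at 2.8 months: (1 − 0.95^3.8)/(1 − 0.95^2.8) = 0.177/0.134 = 1.32.

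Anything beyond this comes from different times to progression.

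**After the change.** With time to first event or end of Period 1 as denominator, 5% per month gives −ln(0.95) = 0.051 per participant-month in both arms, ratio 1.0. Precision stays low. Protocol Table 4 gives 0.2% to 38.5% for 1 of 12. One first event in 24 participant-months (12 × 2 months, assumed) is 4.2 per 100, with an exact Poisson 95% interval of about 0.1 to 23.

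**The case against.** The strongest reply is that the plan sets no between-arm safety objective. Each regimen has its own objective, the analysis is descriptive, and Protocol 9.1 excludes a formal comparison. Duration of therapy by arm lets a reader see an exposure gap, the 60-day death count is a common window, and a Period 1 plus 2 table may follow. With about 12 monotherapy participants, sampling error for a single preferred term can exceed the distortion described here.

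Much of this stands, and it limits how far the point goes. It does not remove it. Duration of therapy is per drug, from first to last dosing day, and is not the adverse event window. The Period 1 plus 2 table adds events that occurred on the combination and is still a percentage. The 60-day count covers deaths only. Small numbers argue for showing intervals; they do not turn a crude percentage into a rate.

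A reader might also infer that the switch rule creates the gap. The documents do not support that. The combination window closes too, 30 days after treatment stops, and progression is a stopping criterion in both arms. The rule removes only the tail, and only for switchers. Tepotinib may continue after investigator-reported progression until the switch (Protocol 4.1), and an event that starts in Period 1 stays there even if it worsens later (SAP Table 10). Assigning events after the first osimertinib dose to monotherapy would be worse.

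**Conclusion.** The omission is real: no TEAE output in SAP 15 or Protocol 9.4.2 takes account of time at risk. If monotherapy is observed for less time, its percentages will be lower at equal risk. Under the assumed 1.5 to 2.5 against 6 to 8 months and a constant hazard of 5 to 10% per month, the apparent ratio is about 2.0 to 4.6. With common events or a smaller exposure gap it is close to 1.

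It would be tempting to conclude that the arms have very different observation times and that monotherapy will therefore look several-fold safer. The documents do not support that as fact. They state no durations, and a several-fold ratio needs both a large exposure gap and events of low or moderate frequency. The constant hazard is likewise an assumption. The point is a worthwhile, inexpensive improvement to reporting. It does not show that the planned tables are invalid for describing each arm on its own.

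**What to change.** In SAP 15.2.2 keep the crude tables and the Period 1 definition. For the overall adverse event summary and the most frequent preferred terms, add by arm:
- the length of the adverse event observation window (start to end of Period 1), which differs from duration of therapy;
- participants with a first event per 100 participant-months at risk, counting time to first event or end of Period 1, with an exact Poisson 95% interval;
- cumulative incidence at 6 and 12 weeks, with the number still at risk.

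The SAP should say how death and other ends of Period 1 are treated in the cumulative incidence.

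The cost is one or two extra tables from dates already collected. The rates assume a roughly constant hazard, which the fixed-time incidences help to check. Intervals for about 12 monotherapy participants will be wide, and the table should show this.
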